## Vital Signs

*Vital signs assessments are performed pre- and post-infusion at all visits with additional triplicate pre- and post-infusion assessments every 6 months as specified on the Schedule of Visits. Vital Sign assessments include body weight, temperature (oral or tympanic, according to the specific medical practice of the Center), pulse, systolic and diastolic blood pressure, and respiratory rate. Height will be measured by a stadiometer in triplicate at each required visit and used along with body weight (also measured in triplicate at each required visit) to calculate Body Mass Index (BMI). Pulse and blood pressure will be measured after the patient has been in the supine position for at least 5 minutes. All results are recorded on the ‘Vital Signs Pre-Infusion’ or ‘Vital Signs Post Infusion’ eCRF pages.*

The baseline value is as described in Section 7.1. The arithmetic mean of all triplicate values is calculated for use in summary tables. Results are converted for summary tables as follows:

- Temperature: Results measured in Fahrenheit converted to Celsius as
  - $\text{Temperature (}^\circ\text{C)} = (\text{Temperature (}^\circ\text{F)} - 32) * 5/9$
- Weight: Results measured in pounds converted to kilograms as
  - $\text{Weight (kg)} = \text{Weight (lb)} / 2.205$
- Height: Results measured in inches converted to centimetre as
  - $\text{Height (cm)} = \text{Height (in)} * 2.54$

The change from baseline is calculated for vital signs with a continuous response at each scheduled post-baseline visit:

- $\text{Change from baseline} = \text{Scheduled Visit result (measured or derived)} - \text{Baseline value.}$

At each scheduled post-baseline visit each vital sign with a continuous response is derived as having a clinically notable change using the rules in Table 5.

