**Table 5: Clinically Notable Values for Vital signs**

| Parameter                      | Unit             | Decrease                               | Increase                                  |
|--------------------------------|------------------|--|---|
| Systolic Blood Pressure (SBP)  | mmHg             | Value $\leq 90$ and $\geq 20$ Decrease | Value $\geq 180$ and $\geq 20$ Increase   |
| Diastolic Blood Pressure (DBP) | mmHg             | Value $\leq 50$ and $\geq 15$ Decrease | Value $\geq 105$ and $\geq 15$ Increase   |
| Sitting Pulse Rate             | bpm              | Value $\leq 50$ and $\geq 15$ Decrease | Value $\geq 120$ and $\geq 15$ Increase   |
| Weight                         | kg               | $\geq 7\%$ Decrease                    | $\geq 7\%$ Increase                       |
| Respiration Rate               | breaths/minute   | $< 12$                                 | $> 25$                                    |
| Temperature                    | $^\circ\text{C}$ | NA                                     | Value $\geq 38.3$ and $\geq 1.1$ Increase |
| Temperature                    | $^\circ\text{F}$ | NA                                     | Value $\geq 101$ and $\geq 2.0$ Increase  |

“Decrease” and “Increase” refer to change from baseline. Respiration Rate is based on recorded value only and not change from baseline.

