### 10.7.6 Vital Signs

All Vital Sign data are included in a listing for the SAF.

Vital Sign results and change from baseline are summarized by summary statistics on scheduled visits for the SAF. The absolute counts (n) and percentages (%) of patients with clinically notable findings are included in a separate summary for the SAF. The absolute counts (n) and percentages (%) of patients with at least one clinically notable change from baseline and summary statistics of the most extreme clinically notable increase and decrease from baseline are presented in separate summaries for the SAF.

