### Laboratory Values

|                  |   |     |   |
|------------------|---|-----|---|
| Table 14.3.2-1.1 | Summary of Hematology Laboratory Parameters         | SAF | U |
| Table 14.3.2-1.2 | Summary of Clinical Chemistry Laboratory Parameters | SAF | R |
| Table 14.3.2-1.3 | Summary of Special Laboratory Parameters            | SAF | R |
| Table 14.3.2-1.4 | Summary of Urinalysis Laboratory Parameters         | SAF | U |

|                     |  |     |   |
|---------------------|--|-----|---|
| Table 14.3.2-2.1    | Summary of Clinically Notable Hematology Laboratory Parameters         | SAF | U |
| Table 14.3.2-2.2    | Summary of Clinically Notable Clinical Chemistry Laboratory Parameters | SAF | R |
| Table 14.3.2-2.3    | Summary of Clinically Notable Urinalysis Laboratory Parameters         | SAF | R |
| Table 14.3.2-3.1    | Summary of Shift in Special Laboratory Parameters from Baseline        | SAF | U |
| Other Safety |  |     |   |
| Table 14.3.3-1.1    | Summary of Culture-Based Sterility Test                                | SAF | U |
| Table 14.3.-1.2     | Summary of Process Events  | SAF | U |
| Table 14.3.3-2.1    | Summary of Vital Sign Data   | SAF | U |
| Table 14.3.3-2.2    | Summary of Clinically Notable Change from Baseline Vital Signs         | SAF | U |
| Table 14.3.3-3.1    | Summary of Physical Examination Data                                   | SAF | U |
| Table 14.3.3-3.2    | Summary of Neurological Examination Data                               | SAF | R |
| Table 14.3.3-4      | Summary of ECG Data  | SAF | U |
| Table 14.3.3-5.1    | Summary of Columbia-Suicide Severity Rating Scale (C-SSRS) Children's  | SAF | U |
| Table 14.3.3-5.1    | Summary of Columbia-Suicide Severity Rating Scale (C-SSRS) Adult's     | SAF | R |
| Table 14.3.3-6.1    | Summary of Bone Mineral Density z-scores                               | SAF | U |
| Table 14.3.3-6.2    | Summary of Shift in Bone Mineral Density z-scores from Baseline        | SAF | U |
| Table 14.3.3-7.1    | Summary of Tanner Staging data   | SAF | U |

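### Respiration rate is flagged on the recorded value alone but reported as a notable change from baseline, so a reported increase can be zero or negative and a reported decrease can be a rise

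*SAP*

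**What the plan says.** SAP 7.4.8 (Vital Signs) gives the rule, applied visit by visit after baseline: "each vital sign with a continuous response is derived as having a clinically notable change using the rules in Table 5". That table has one column for decreases and one for increases, and its footnote explains that these headings denote a change relative to baseline, but that "Respiration Rate is based on recorded value only and not change from baseline". Blood pressure, pulse and temperature need both a level and a change of a set size. Weight needs a percentage change. Respiration rate has a level only: below 12 in the decrease column, above 25 in the increase column.

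SAP 10.7.6 promises, as counts with percentages, a summary that covers "patients with at least one clinically notable change from baseline and summary statistics of the most extreme clinically notable increase and decrease from baseline". The table list in SAP 12.1 carries this as Table 14.3.3-2.2, "Summary of Clinically Notable Change from Baseline Vital Signs". Neither place excepts respiration rate.

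SAP 10.7.6 also says that counts of "patients with clinically notable findings are included in a separate summary for the SAF". Section 12.1 has no entry under that description: the only vital-signs tables listed are 14.3.3-2.1 (all vital-sign data) and 14.3.3-2.2.

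**The concern.** A rule based on value alone feeds an output labelled as change. A patient who breathes fast at baseline and stays above 25 is reported as having a notable increase, even when the rate is unchanged or has come down. The mirror case holds below 12. The same output summarises the most extreme increase and decrease, and for respiration rate those statistics can have the wrong sign.

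The label matters because changes in vital signs are part of the primary safety endpoint (SAP 3.4; protocol 7.3) and the study has a single arm. No concurrent control would show a similar count arising from breathing rates that were already high. The protocol's description of the disease includes chronic pulmonary infection and chronic lung disease, and the SAP's age categories start at 6 years, so some baseline values above 25 are plausible. Exclusion criterion 7 (severe or unstable pulmonary disease) makes them less common.

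**Working it through.** The plan states no figure to reproduce. The check applies the rule as written and then gauges how often the problem could arise.

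**1. Respiration rate under Table 5 as written**

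| Baseline | Visit | Change | Flag as written | Flag if the visit must also lie beyond baseline |
|---|---|---|---|---|
| 28 | 28 | 0 | Increase | none |
| 28 | 26 | -2 | Increase | none |
| 32 | 27 | -5 | Increase | none |
| 11 | 11 | 0 | Decrease | none |
| 9 | 11 | +2 | Decrease | none |
| 18 | 28 | +10 | Increase | Increase |
| 26 | 40 | +14 | Increase | Increase |
| 18 | 11 | -7 | Decrease | Decrease |

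A falling rate is counted as an increase only while the visit value is still above 25.

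**2. Other rows, same test**

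Systolic pressure 185 to 185 and 190 to 182: no flag. Pulse 125 to 125 and 130 to 122: no flag. Temperature 38.5 to 38.5: no flag. Each of these rows requires a change in the stated direction, so the fault is confined to respiration rate. The change itself is available for it: "The change from baseline is calculated for vital signs with a continuous response at each scheduled post-baseline visit".

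**3. Possible size, high side**

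The documents give no respiration distribution, so every input here is an assumption. Patient mean μ ~ Normal(m, s_b²), with m = 18, 20, 22 and s_b = 2.5, 3, 3.5. Baseline b = round(μ + e₀) and visits v_k = round(μ + e_k), k = 1 to 12, with e ~ Normal(0, s_w²) and s_w = 1.5, 2, 2.5. There is no true change. This gives 27 settings of 200,000 patients each.

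- *Reading level:* the number of readings with v_k > 25 and v_k ≤ b, divided by the number with v_k > 25. Central setting (20, 3, 2): about 26%. Over the grid: 10% to about 42%.
- *Patient level*, the unit that SAP 10.7.6 reports: the share of all patients with at least one v_k > 25 but none that is also above b. Central setting: 1.8%. Over the grid: 0.2% to about 4.7%.
- In the central setting 24.2% of patients have some flag, so 1.8 / 24.2 ≈ 7% of flagged patients never exceed their own baseline on a flagged reading. With a direction condition, 24.2 − 1.8 = 22.4% would still be flagged.

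At the protocol's maximum of 150 patients this is 150 × 0.018 = 2.7 patients, with a range from 150 × 0.002 = 0.3 to 150 × 0.047 ≈ 7. Repeating the simulation moves the patient-level figures by about 0.1 percentage point.

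**The case against.** The strongest reply is that the rule is declared. The footnote states the exception openly, Table 5 is titled as notable values, and a value-only limit is a legitimate choice. That stands as a defence of the rule. It does not correct SAP 10.7.6 or the title of Table 14.3.3-2.2, and a reader of that table sees only a change from baseline.

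Second, protocol 13.2 refers to Appendix 4 for guidance on notable vital-sign values. That appendix is not in the text available here, so the respiration rule may come straight from it. This also stands, and is why it should be checked before any edit.

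Third, the harm is limited. The analysis is descriptive, one parameter is affected, and SAP 10.7.6 also plans results and change from baseline by visit plus a full listing. All true, and it keeps the point small.

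Two stronger readings are tempting. A reader might infer that the table heavily inflates on-treatment respiratory change. Comparing the SAP rule with one that requires baseline to be 25 or lower gives excess patient counts of 0.4 to 20 percentage points. That comparison largely reflects the assumed share of patients above 25 at baseline, and it treats real worsening from such a baseline as error. A reader might also quote the reading-level share as the size, but the output counts patients. The documents contain no baseline respiration data to support either inference.

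**Conclusion.** The inconsistency is real and follows from the text alone: a flag that ignores baseline is reported as a change from baseline, in both directions, with no exception. That part needs no assumption.

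Its size is modest and not known. Under the assumed distributions, with 12 post-baseline readings and no true change, roughly 0 to 7 of 150 patients would be counted as a notable increase without any flagged reading above their own baseline (about 3 in the central setting). The low side was not simulated. The documents do not support saying that the limits of 12 and 25 are wrong, that the rule is concealed, or that the primary safety assessment is unsound. This is a mismatch between rule and label for one vital sign, worth correcting before the table is produced.

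**What to change.** First check the respiration rule against protocol Appendix 4. Then reconcile Table 5, SAP 10.7.6 and Table 14.3.3-2.2 in one of two ways, keeping the sponsor's limits:

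- **Report as a value.** Show respiration rate only in the notable-findings summary that SAP 10.7.6 already promises, add that summary to the list in SAP 12.1, and remove respiration rate from Table 14.3.3-2.2. Cost: one table entry.
- **Add a direction condition.** Keep respiration rate in Table 14.3.3-2.2, but count an increase only if the visit value is above 25 and above the patient's own baseline, and a decrease only if it is below 12 and below baseline. Cost: one programming condition and a footnote edit. This corrects the sign only: a move from 25 to 26 still counts.

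Do not instead require baseline to lie within the limits. That would drop real worsening, such as 26 to 40, in patients who start high.

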### **Physical and Neurological Examination**

*Physical examinations are performed as specified on the Schedule of Visits. Physical examination includes an examination of general appearance, skin, neck (including thyroid), eyes and ears, nose, mouth, throat, lungs, heart, abdomen, back, lymph nodes, extremities and nervous system. Abnormal results are identified by the investigator and specified as clinically significant or not clinically significant. All results are recorded on the ‘Physical Examination Pre-Infusion’ or ‘Physical Examination Post Infusion’ eCRF pages. Neurological Examination results are recorded on the ‘Neurological Examination’ eCRF page.*

Physical Examinations are performed post infusion at all visits with additional pre-infusion assessments at Month 6, Month 12 etc. Neurological Examinations are performed pre-infusion at Month 6, Month 12 etc.

### **ECG variables**

Electrocardiogram (ECG) evaluations are performed every 6 months in accordance with the Schedule of Study Events. At each evaluation, three ECG assessments are performed in succession, approximately 10 minutes apart. The investigator’s interpretation of ECG results (‘normal’; ‘abnormal, clinically significant’; ‘abnormal, not clinically significant’) is recorded on the ‘ECG’ eCRF page.

### **C-SSRS**

The Columbia Suicide Severity Rating Scale (C-SSRS) is a suicidal ideation rating scale which rates individual’s degree of suicidal ideation on a scale, ranging from "wish to be dead" to "active suicidal ideation with specific plan and intent." (Posner, et al., 2011). At each visit, patients are assigned an ideation severity score of 0 (no ideation present) to 5 (active suicidal ideation with plan and intent) based on their most severe suicidal ideation since the last visit as recorded in the eCRF. This is derived as 0 if the question “Wish to be dead” is marked as “No” and is derived as 1 to 5 based on the response to “Most severe ideation (Type#(1-5))”. If one of the two variables is missing for a visit, the ideation severity score is also regarded as missing.

Patients under the age of 12 years at the baseline visit would use the pediatric version of the scale throughout the study. Results are recorded on the ‘C-SSRS Children’s Since Last Visit’ or ‘C-SSRS Adult’s Since Last Visit’ eCRF page as appropriate.

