### 5.2 CDISC

All output as defined in the SAP is generated based on CDISC ADaM datasets, as per contract with EryDel. Specifications for the ADaM datasets as well as the underlying SDTM datasets are described in separate documents. CDISC SDTM datasets are produced based on SDTM version 1.4 with the SDTM implementation guide version 3.2, CDISC ADaM datasets are produced based on ADaM version 2.1 with the ADaM implementation guide version 1.0. Define.xml is produced based on version 2.0.

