#### **10.7.9 C-SSRS**

All recorded C-SSRS data are included in listings for the SAF.

The ideation summary score is summarized at each scheduled visit as a continuous variable, Additionally the ideation summary score is analysed as a categorical variable. Both analyses are performed separately for the Children's scale and the Adult's Scale as described in section 8.1 on the SAF.

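### The C-SSRS ideation score rules in SAP 7.4.8 do not reliably produce the score that the same paragraph defines

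*SAP*

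**What the plan says.** The C-SSRS paragraph of SAP 7.4.8 first defines the score: "At each visit, patients are assigned an ideation severity score of 0 (no ideation present") at the bottom and 5 for active ideation with plan and intent at the top, "based on their most severe suicidal ideation since the last visit as recorded in the eCRF".

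It then gives three operating rules:

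- The score is 0 when 'Wish to be dead' is answered No.
- Otherwise the score "is derived as 1 to 5 based on the response to" the most severe ideation field, which is labelled Type#(1-5).
- "If one of the two variables is missing for a visit, the ideation severity score is also regarded as missing".

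SAP 10.7.9 sets out the use of the score: "The ideation summary score is summarized at each scheduled visit as a continuous variable". It is also tabulated as a categorical variable. "Both analyses are performed separately for the" Children's and Adult's versions of the scale. The same section adds: "All recorded C-SSRS data are included in listings for the SAF".

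SAP 8.1 makes two statements about percentages. One bases relative frequencies on all observations. The other bases percentages, unless otherwise specified, on patients with data. SAP 5.3 has the ADaM datasets double-programmed and checked against the SAP.

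**The concern.** The definition is about the most severe ideation of any type. The 0 rule, however, tests only 'Wish to be dead', which the same paragraph describes as the lowest step of the scale. The missing-data rule requires both fields to be present and states no exception. Three kinds of record therefore need attention:

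- **(a)** 'Wish to be dead' is blank but a type is recorded. The most severe ideation is known, yet the score is set to missing.
- **(b)** 'Wish to be dead' is No and a type is recorded. The 0 rule and the type rule both apply, and the derivation does not say which wins. If the 0 rule is programmed first, recorded ideation is tabulated as none.
- **(c)** 'Wish to be dead' is No and the type is blank because there was no ideation. Read literally, the score is missing, although the definition gives 0. This arises only if the eCRF leaves the type field blank in that situation.

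Protocol 13 lists C-SSRS among the safety assessments. It is collected at every monthly visit after baseline and at safety follow-up. Protocol 13.7 says subjects with suicidal ideation will be excluded, so 0 should be the usual score, and 0 is the category that (c) can remove. What is at stake is whether the by-visit summaries show the defined score.

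**Working it through.** The SAP states no figure to reproduce. The check applies its three rules to every possible input and compares each result with the SAP's own definition.

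**Inputs (SAP 7.4.8).** 'Wish to be dead': Yes, No or blank. Type: blank or 1 to 5. Number of pairs = 3 × 6 = 18.

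| 'Wish to be dead' | Type | Pairs | SAP rules, read literally | SAP definition |
|---|---|---|---|---|
| Yes | 1-5 | 5 | that type | that type |
| No | 1-5 | 5 | 0 and that type both apply | recorded type |
| blank | 1-5 | 5 | missing | recorded type |
| No | blank | 1 | missing | 0, if no other ideation item is endorsed |
| Yes | blank | 1 | missing | at least 1; type may be recoverable from item-level answers |
| blank | blank | 1 | missing | missing, unless item-level answers decide it |

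Missing: 5 + 1 + 1 + 1 = 8. Scoreable: 18 − 8 = 10, made up of 5 with a single score and 5 in conflict. All 10 carry a recorded type. So, unless the eCRF has a code for 'none', no ideation-free record reaches 0 under the literal rules. These are counts of input patterns, not of patients.

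**Direction of (c).** Let N be the patients assessed at a visit, k those with ideation, and b the ideation-free patients set to missing (0 ≤ b ≤ N − k).

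- Percentage among patients with data: k/(N − b), which exceeds k/N whenever k ≥ 1 and b ≥ 1.
- Mean: sum of types/(N − b), larger by the factor N/(N − b).
- Percentage on all observations (the other SAP 8.1 sentence): k/N is unchanged, while the score-0 row falls from (N − k)/N to (N − k − b)/N.

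*Illustration of the range, on assumed values.* Take N = 150, the maximum entry expected in Protocol 16.2.1, and k = 3, all recorded as Yes with type 1. If b = 0, the ideation percentage is 3/150 = 2.0% and the mean is 3/150 = 0.02. If b = 150 − 3 = 147, they are 3/3 = 100% and 3/3 = 1.0. If k = 0 and every type field is blank, every score is missing. The documents do not say where in this range b falls, and the split into Children's and Adult's tables would make each N smaller.

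**Direction of (a) and (b).** These work the other way.

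- (a) If j of the k patients lose a known type, the percentage among patients with data is (k − j)/(N − j), below k/N whenever j ≥ 1 and k < N.
- (b) If c patients with a recorded type are scored 0, it is (k − c)/N, also below k/N. If the type rule is applied first, (b) does no harm.

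**The case against.** The strongest reply is that this is a wording gap that the process will absorb.

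- **The eCRF may settle (c).** Type#(1-5) is a field label, not a code list. A stored 'none' value would remove (c). A programmer might also treat a field that does not apply as not missing, which fits the stated purpose of the 0 rule.
- **Other documents may settle the rest.** On the datasets, SAP 5.2 says: "Specifications for the ADaM datasets as well as the underlying SDTM datasets are described in separate documents". SAP 5.1 refers data quality control to the Data Management Plan and its Data Validation Plan. None of these is available here.
- **Quality control.** SAP 5.3 adds double programming, a sensibility review and an independent senior review. A visit with no zeros would be hard to overlook.
- **Rarity and consequence.** Cases (a) and (b) need unusual records, and nothing shows that they occur. The tables are descriptive, SAP 9 says there are no hypothesis tests, and C-SSRS is not named in the primary endpoint (SAP 3.4).

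Most of this stands, and it limits the point. It does not remove it. Cases (a) and (b) do not depend on how an ideation-free page is completed. Dataset QC is against the SAP, so correct code would depart from its reference while literal code would agree with it. Double programming does not decide which of two applicable rules was intended.

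A reader might infer more than the documents support:

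- *That the tables will lose their zeros or show 100% ideation.* That requires an eCRF coding that the documents do not show.
- *That 8 of 18 is an error rate.* It weights an improbable entry the same as the commonest one.
- *That all 8 missing pairs are settled one way or the other.* Yes with a blank type may be resolvable, because SAP 12.3 lists item-level ideation data.
- *That a suicidality signal would be hidden or the primary safety conclusion compromised.* All recorded C-SSRS data are listed, and no conclusion in the plan is shown to turn on this score.

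**Conclusion.** The point holds in a limited form. SAP 7.4.8 states rules that do not reliably give the score it defines, and no other section supplied corrects them. Case (a) follows from the text alone. Case (b) is an unresolved conflict on the text alone and does harm only if the 0 rule takes precedence. Case (c) is conditional on the type field being blank when there is no ideation and on a literal reading of the missing-data rule.

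The direction is known: (a), and (b) if the 0 rule comes first, understate ideation, while (c) overstates it among patients with data. The size is not known, because the frequency of these records is not in the documents. The reach is the descriptive by-visit C-SSRS tables for the Children's and Adult's scales. The point is worth correcting because the rule is stated, checkable and cheap to repair, not because a material distortion has been shown.

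**What to change.** Replace the derivation in SAP 7.4.8 with the following order of rules:

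1. If a most severe ideation type (1-5) is recorded, the score is that type, whatever the answer to 'Wish to be dead'.
2. If no type is recorded and the recorded ideation items show no ideation ('Wish to be dead' = No with no other ideation item endorsed, or a 'none' code if the eCRF has one), the score is 0. A type field left blank for this reason is not missing data.
3. If ideation is endorsed and the type field is blank, use the highest type endorsed at item level, where available.
4. Otherwise the score is missing.

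Flag inconsistent records, such as No with type 1, in the listing and handle them under the existing data-validation process. Scoring such a record by its type is a choice, so the SAP should state it openly.

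With these rules all 15 pairs that carry a type (3 × 5) give one score, and the 3 pairs without a type are decided by the item-level answers or a 'none' code where these exist. The cost is a few sentences in the SAP and one ADaM derivation, with no new data collection.
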